
Conclusion: This will be the 1st human laboratory study to evaluate combinations of cannabinoids and opioids on a comprehensive and validated quantitative sensory testing battery, and the results of this study will identify whether a signal for this medication combination exists that should be advanced into randomized controlled trial evaluations with clinical pain populations. This study will also assess aspects that would impact drug development (abuse liability, neurocognitive impairment) and the effect of participant sex on outcomes. The ultimate goal of this research will be to determine which medication/dose combinations may exert strong analgesic effects, while minimizing abuse liability and cognitive deficits, in order to advance these medications into clinical trials for the treatment of chronic pain. This is a logical first step towards evaluating combined cannabinoid/opioids treatments for chronic pain, and will provide data necessary to support numerous evaluations of combination treatments for this population.

4. Study Procedures

- a. Study design, including the sequence and timing of study procedures (distinguish research procedures from those that are part of routine care).

Project Overview: This study will enroll 100 healthy adults, and will aim to complete 60 (30 men, 30 women) participants. Participants will conduct a within-subject evaluation of the degree to which the FDA-approved cannabinoid dronabinol (Marinol) enhances the analgesic effect of the prototypic opioid hydromorphone (Dilaudid). Subjects will complete a Screening visit to establish study eligibility and 5 experimental sessions. Experimental sessions will occur approximately once weekly and will permit subjects to admit themselves into the clinical research unit the night before the session if interested. Subjects will be provided with taxi service to and from the session. Subjects will receive a dose of hydromorphone (4mg, oral) and a double-blind oral dose of study drug or placebo the

morning of each experimental session, and will undergo QST measures of laboratory evoked pain, provide self-report ratings of drug effects, and complete a neurocognitive battery. The order of sessions will be randomized with the exception of Session 1, which will always be active hydromorphone + placebo to ensure the participant has a safe response to hydromorphone before proceeding into the remaining sessions.

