The morning of each experimental session, the subject will receive a calorie-controlled breakfast each morning. Following breakfast, subjects will complete a baseline rating of QST and self-report measures (from which all subsequent ratings will be compared for data analysis purposes). An oral capsule containing either study drug or placebo will then be administered and hydromorphone (4mg oral in four sessions and a placebo oral dose in one session) will be administered. The time of drug administration will be selected to enable both dronabinol and hydromorphone to exert peak effects at the same time. Subjects will complete QST (see below) and self-report measures at regular intervals following study drug administration. Self-report measures will include specific opioid agonist and antagonist effects, to assess whether cannabinoids are exerting an effect on a particular category of opioid agonist symptom, and will capture whether any negative effects (e.g., nausea) occur as a function of the cannabinoid dose. Frequent collection will enable evaluation of time to peak drug effects, duration of effects, and general time course of effects and is a widely used and accepted approach in laboratory studies of drug effects. During the final assessment each day, subjects will complete a Drug vs. Money Questionnaire to indicate the dollar value they would place upon the drugs received⁹⁸. This is a well-accepted proxy measure of abuse liability. Study staff will document adverse events throughout the study and any subject who experiences a strongly unpleasant effect of the medications will be able to end participation. Any subject who is experiencing strong agonist effects at the end of the session will be provided overnight accommodation in the CRU; based on our experience we expect this to be minimal and are budgeting for 10% of sessions to have a 2nd night.

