We have included placebo control conditions for each study drug, to assist with interpretation of the study results. Since this study will recruit healthy individuals and we will not be removing access to a known treatment, we believe that inclusion of the placebo conditions poses low risk to participants.

- f. Definition of treatment failure or participant removal criteria.

Participants will be removed from the study if they remove their consent to participate, become pregnant, refuse to adhere to the study session schedule, or if it becomes clear that their continued participation could put them at increased risk (e.g., develop a chronic pain condition that requires treatment, onset of a medical/psychiatric disorder). These decisions will be made in conjunction with the BPRU medical team.

- g. Description of what happens to participants receiving therapy when study ends or if a participant's participation in the study ends prematurely.

N/A

5. Inclusion/Exclusion Criteria

Inclusion Criteria:

- Aged 18-75
- Urine sample tests negative for common illicit substances of abuse, including cannabis
- Medically cleared to take study medications

- Are not pregnant or breast feeding
- Willing to comply with the study protocol.

Exclusion Criteria:

- Meet DSM-5 criteria for alcohol/substance use disorder
- Taking opioids for pain
- Previous adverse reaction to a cannabinoid product
- Prescribed and taking stimulants or benzodiazepines
- Answer “yes” to item 1 of the Brief Pain Inventory indicating chronic pain
- Self-report any illicit drug use in the past 7 days
- Presence of any clinically significant medical/psychiatric illness judged by the investigators to put subject at elevated risk for experiencing an adverse event
- History of seizure disorder
- Have a known allergy to the study medications or sesame seed oil
- Taking medications contraindicated with hydromorphone or dronabinol
- Have a history of clinically significant cardiac arrhythmias or vasopastic disease
- Have an abnormal and clinically-significant ECG
- Failure to discriminate between hydromorphone and placebo in the Screening 2/Qualifying session.

6. Drugs/ Substances/ Devices

- a. The rationale for choosing the drug and dose or for choosing the device to be used.

Study Drugs: Hydromorphone and dronabinol will be over-encapsulated by our research pharmacy and administered orally.

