Hydromorphone (Dialudid) is a potent mu-opioid agonist that we have extensive experience administering in controlled laboratory settings. Hydromorphone is not subject to differences in CYP metabolic enzymes (in contrast to other opioids such as oxycodone) and therefore will not require us to screen out individuals with recent exposure to CYP inhibitors/inducers, or to analyze/statistically control for CYP metabolic profiles. We have selected a 4mg oral hydromorphone dose for this study because we have data from another ongoing study (IRB00047423) indicating it produces a mild-moderate effect (versus a ceiling or floor effect) and will therefore allow us to visualize changes as a function of the dronabinol. 4mg oral hydromorphone is also a dose that is commercially available and regularly prescribed for analgesia, which increases the clinical relevance of this study. Based on clinical experience, we expect it to produce a moderate analgesic effect on pain. This is an important feature because too strong a dose could overwhelm the cannabinoid effect and prevent us from effectively evaluating the study hypotheses. A moderate dose of hydromorphone will better enable us to evaluate shifts in the analgesic curve as a function of the study drug, and provide a stronger assessment of whether cannabinoids will enhance the analgesic effect of hydromorphone.

Study Drug Dosing		
Condition	Hydromorphone Oral	Dronabinol Oral
Nonrandomized 1	4mg	Placebo
Randomized 2	4mg	2.5mg
3	4mg	5mg
4	4mg	10mg
5	placebo	placebo
Session 1 will be nonrandomized and used as a safety screening day. Sessions 2-5 will be randomized and counter-balanced across participants.		

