- **Primary Aim 1:** The primary outcome will be the area under the curve of each QST procedure, which will provide an assessment of the mean duration and magnitude of the drug effect. Primary outcomes will be tested with repeated two-factor (Drug Condition x Time) models to examine main and interaction effects for all raw data as designed. If there is large variation across subjects at the baseline timepoint, the raw data will be transformed as a change from baseline and analyzed in drug condition by time models. Statistical analyses will be conducted using multilevel analyses with an autoregressive covariance structure using SAS PROC MIXED Software¹³¹. These analyses will permit an examination for effects of drug condition and time effects associated within the course of the study. Interpretation of drug condition main effects and interactions will rely on Tukey post-hoc tests. This aim will also assess frequency of adverse events as a function of study drug.

Specific outcome variables for the QST procedures will be as follows:

- a. Heat Pain Threshold and Tolerance: HPT_h and HPT_o in °C (both in normal and capsaicin treated skin)
 - b. Pressure Pain Threshold: PPT_h in kilopascals
 - c. Thermal and Mechanical Temporal Summation: Verbal pain ratings (both in normal and capsaicin treated skin for MTS)
 - d. Conditioned Pain Modulation: The index score of CPM:PPT_h and CPM:TS (compared to baseline) for each dose
 - e. Cold Water Tolerance: Time to tolerance (compared to baseline) for each dose.
- **Primary Aim 2:** The Drug vs. Money questionnaire will be compared across dose conditions, using peak monetary rating for each dose as the primary outcome. Within-subject changes, as a function of dose, will be analyzed using a repeated measures analysis of variance (ANOVA).
 - **Primary Aim 3:** Neurocognitive tests will be compared as a function of study drug dose, using study session number (1-6) as a covariate to control for practice effects. Specific outcome measures will include:
 - a. Divided Attention Task (DAT): Accuracy with which they perform the two tasks
 - b. Digit Symbol Substitution Task (DSST): Accuracy, total number of patterns completed in allotted time
 - c. Computerized version of the Paced Auditory Serial Addition Task (PASAT): Summed of correct trials

b. Secondary outcome variables.

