a. Protection Against Hydromorphone Risks: We have extensive experience in the administration of hydromorphone and other opioid agonists in controlled laboratory settings and therefore anticipate few problems. Any individual who may be prone to the risks associated with hydromorphone will be excluded from participating. Although research staff and participants will be blinded to the exact medication provided, both groups will be informed of the potential side effects and risks associated with the study drug administration. Participants will be free to discontinue study participation at any time without consequence. The dose of hydromorphone that is being administered is consistent with clinical care, and is a medium level dose for the treatment of pain. Further, The Qualifying Session provides us a unique opportunity to assess for sensitivity to hydromorphone, and any participant who shows intolerance to hydromorphone during the Qualifying Session will be excluded from the primary study. Great care has been taken in selecting the appropriate drug doses to ensure hydromorphone is well-tolerated and safe for our participants and participants will also be able to discontinue study participation at any time. The most serious risk associated with hydromorphone administration is respiratory depression. We believe this risk is minimal in this study for several reasons. First, we are administering a mid-level dose and have extensive experience administering

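### Aim 2's repeated-measures ANOVA would conventionally discard everyone who misses a session, although Session 1 is both the safety gate and the only hydromorphone-alone reference

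*Combined protocol and SAP*

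**What the plan says.** - **Analysis.** Section 7a, Primary Aim 2, takes the peak Drug vs. Money rating per dose and states: "Within-subject changes, as a function of dose, will be analyzed using a repeated measures analysis of variance (ANOVA". Primary Aim 1 in the same section names multilevel models in PROC MIXED. Primary Aim 3 names no model. No analysis set or missing-data rule is given for any aim.
- **Reference and gate.** Section 4a (Project Overview) describes Session 1 as the session "which will always be active hydromorphone + placebo to ensure the participant has a safe response to hydromorphone before proceeding into the remaining sessions". The note to the dosing table in section 6a adds: "Session 1 will be nonrandomized and used as a safety screening day". In that table it is the only row with active hydromorphone and no dronabinol. Section 2 states the Aim 2 hypothesis as no increase compared with hydromorphone alone.
- **Ways out.** Section 4a (Experimental Sessions) says that "any subject who experiences a strongly unpleasant effect of the medications will be able to end participation", which applies to every session. Section 8b says that "any participant who shows intolerance to hydromorphone during the Qualifying Session will be excluded from the primary study". Section 5 lists as an exclusion: "Failure to discriminate between hydromorphone and placebo in the Screening 2/Qualifying session". Section 4b schedules one screening visit and five experimental sessions, with no separate qualifying session.
- **Expected loss.** Section 4a: "This study will enroll 100 healthy adults, and will aim to complete 60". Section 7c instead plans 60 enrolled for 50 completers.

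**The concern.** A conventional repeated-measures ANOVA needs a value in every condition. Someone who stops after Session 1 supplies a reference value and nothing else, so that value is lost. Someone who stops later loses usable dronabinol data as well.

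The first consequence is wasted precision. The second is possible bias. If people stop partly because of how Session 1 itself went, completers' reference values are a selected set, and their later sessions drift back towards their usual level. The contrast that Aim 2 rests on then moves without any drug effect. This matters because Aim 2 seeks reassurance about abuse liability, and Aim 1 already has a method that can keep the discarded data. The point is separate from session order and would remain if there were no order effect.

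**Working it through.** **1. The plan's own figure.** Section 7c gives n = 45 for power 0.95, effect size 0.2 and six conditions. Assume α = 0.05, correlation ρ = 0.5 and sphericity (none is stated). Then λ = f²nm/(1−ρ) = 0.04 × 45 × 6 / 0.5 = 21.6 on 5 and 220 df. Power is 0.962, and the smallest n reaching 0.95 is 43. The stated 45 reproduces to within two. (With the five conditions in the dosing table, 45 gives 0.937 and 48 are needed.) So 0.2 reads as Cohen's f. Over six conditions that implies a largest mean difference of at least 2 × 0.2 = 0.4 SD, and a bias in SD units should not be set directly beside 0.2.

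**2. Planned loss.** 1 − 50/60 = 16.7%; 1 − 60/100 = 40%.

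**3. Bias of the completer contrast.** Assume no true difference, unit variance, equal correlation ρ between sessions, and a share q stopped after Session 1 because they are lowest on an index correlated r with the Session 1 value. None of q, r or ρ is in the documents. Let k = φ(z_q)/(1−q). Completers' Session 1 mean rises by r·k and their later means by ρ·r·k, so

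bias = −(1−ρ)·r·k.

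For q = 10%: k = 0.1755/0.90 = 0.195, and −0.5 × 0.5 × 0.195 = −0.049.

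| Stopped after Session 1 | k | ρ = 0.5, r = 0.5 | ρ = 0.5, r = 1 |
|---|---|---|---|
| 5% | 0.109 | −0.027 | −0.054 |
| 10% | 0.195 | −0.049 | −0.097 |
| 16.7% | 0.300 | −0.075 | −0.150 |
| 20% | 0.350 | −0.087 | −0.175 |
| 40% | 0.644 | −0.161 | −0.322 |

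The r = 1 column is an upper value, because it makes the Session 1 value the sole cause of stopping. The 40% row is also a limit, because it treats all attrition as Session 1 stops.

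**4. What changes the sign or size.**
- If those stopped place a high value on the drug (r = −0.5, ρ = 0.5), the bias is +0.049, +0.075 and +0.161 SD at 10%, 16.7% and 40%.
- With 10% stopped after Session 1 plus 3%, 5% or 10% stopped after each dronabinol session by the same mechanism (r = ρ = 0.5), simulated net bias is −0.03, −0.02 and 0.00 SD.

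**5. Mixed model keeping Session 1 data.**
- If stopping depends on the observed Session 1 value plus noise, simulated bias is 0.00 at 10%, 16.7% and 40%.
- If stopping reflects a stable trait, completers have bias 0.00 and the mixed model is off by (1−ρ)·√ρ·r·k. At 10%, with r = ρ = 0.5, this is 0.5 × 0.707 × 0.5 × 0.195 = +0.034 (about +0.04 in simulation). At 16.7% and 40% it is +0.05 and about +0.12 SD.

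**6. Precision under random exit, ρ = 0.5.** For one dose against the reference, with N dosed and n completers, the completer SE is √(2(1−ρ)/n). If every exit follows Session 1 directly, the mixed-model SE is √((1−ρ²)/n + (1−ρ)²/N).
- 60 to 50: √0.0200 = 0.1414 against √(0.0150 + 0.0042) = 0.1384, so the completer SE is 2% larger.
- 100 to 60: √0.0167 = 0.1291 against √(0.0125 + 0.0025) = 0.1225, so it is 5% larger.

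Later exits leave more data to recover. Generalised least squares on all available sessions, with exits spread evenly after Sessions 1 to 4, gives 0.1341 and 0.1107 (completer SE 5% and 17% larger). With every exit after Session 4 it gives 0.1308 and 0.1033 (8% and 25% larger). Simulated random exit gave a mixed-model SE about 6% smaller for 60 to 50 and about 11% smaller for 100 to 60. I use 6–11% as a mid-range figure.

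**The case against.** A reader might infer that the ANOVA is biased towards the hoped-for finding of no increase. The documents do not support that.

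- **Direction.** The gate is safety, not a low Drug vs. Money value. The monitoring triggers in sections 7d and 8b are physiological: blood pressure, heart rate, respiration with sedation, and oxygen saturation. Section 8a lists both dysphoria and euphoria as common. Removing low-value, unpleasant responses pushes the contrast down. Removing strong agonist responders can push it up. Stops after dronabinol sessions partly cancel the first effect. This objection stands in full.
- **Selection alone is not bias.** All five conditions are estimated in the same completers, so stable intolerance limits generalisability but leaves the contrast unbiased. It then shifts the mixed model slightly. This stands, and it is why completers should stay as a sensitivity analysis.
- **Inference.** No passage says that incomplete participants are dropped; that follows from the usual form of the method. No Session 1 criterion based on subjective response is given. The explicit intolerance exclusion belongs to a Qualifying Session; if that is separate from Session 1, this route does not act on the reference value.
- **Attrition and data.** Consent is signed at the start of screening, so the 100 may include people never dosed. Drug vs. Money is completed at the last assessment of the day, so someone who leaves mid-session may have no value.

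What remains is that the gate and the reference are the same session, that the named method conventionally discards usable data, and that the plan already contains a method that does not.

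**Conclusion.** The concern holds as a choice of analysis with a certain but moderate cost and a possible small bias of unknown sign. If the ANOVA is run in its conventional form, the Aim 2 standard error is roughly 6–11% larger than under a mixed model. That assumes random exit at the planned attrition and ρ = 0.5, and it varies with when people leave. The bias is about −0.05 SD at 10% stopped with r = ρ = 0.5, and it reverses if strong agonist responders are those who stop. Values of −0.05, −0.10 and −0.175 SD at 5%, 10% and 20% stopped are upper values for ρ = 0.5. Nothing in the documents shows that Aim 2 is tilted towards its hypothesis. The change is still worth making, because it recovers data at almost no cost.

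**What to change.** 1. In section 7a, analyse Aim 2 with the PROC MIXED approach already specified for Aim 1, and name the same approach for Aim 3. State the covariance between sessions; the figures here assume equal correlation.
2. Define the analysis set as every participant with at least one dosed session, keeping the Session 1 data of those who stop.
3. Report the completer analysis as a sensitivity analysis, since the two methods fail under different reasons for stopping.
4. Report the number of Session 1 stops and the reasons, with any Drug vs. Money values available.
5. Reconcile the Qualifying Session in sections 5 and 8b with Session 1 in sections 4a and 6a, and the 100-to-60 figures with the 60-to-50 figures.

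The cost is SAP wording: the same software and no new data. The small downside is reliance on a missing-at-random assumption. The change does not cure the separate problem that the reference condition always comes first.

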- Discomfort Intolerance Scale: A 7-item self-report measure of tolerance to distressing situations.

Session Measures:

- Clinical Opiate Withdrawal Scale: A widely used, 11-item observer-rating of opioid withdrawal symptoms.
- Vital Signs: We will assess blood pressure, pulse, respiration, and oxygen saturation.
- Pupillary Diameter: Pupil size will be assessed using an electronic Neuroptics Pupilometer
- Visual Analog Rating Scales: Participants will rate the subjective reports of drug effects items on a scale of 0 (none at all) to 100 (strongest possible), including items such as good effects, bad effects, high, withdrawal, sick, like how I feel, nausea, sedation, feel sleepy.
- Opioid Agonist/Antagonist Rating Scale: This questionnaire assesses positive and negative effects of opioids.
- Drug vs. Money Questionnaire: This questionnaire is a frequently used measure to assess relative monetary value of a drug and is being used to assess relative reinforcing effects of the drug compared to hypothetical monetary values.

Computer-based Cognitive Tests:

- Divided Attention Task (DAT): Participants simultaneously perform two different simple tasks based on visual stimuli presented on a computer screen. This task is computer based.
- Digit Symbol Substitution Task (DSST): Participants must hand type patterns presented to them on a computer screen for 90 seconds
- Paced Auditory Serial Addition Task (PASAT): Participants are provided a string of single digit numbers on the computer and must add the total of the prior to integers presented and respond by selecting the answer using the computer mouse on the screen.

Participants will also be asked to provide an optional blood sample that will be banked with the Genetic Resources Core Facility. Samples will be analyzed at a later date and governed by a separate hypothesis-driven IRB protocol. Genetic sample collection will be optional and will not impact primary study eligibility.

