Demographic and drug use characteristics, including a positive signal (defined as >20 points rating from baseline on VAS rating of Drug Effect from Session 1), that are hypothesized a priori to be associated with outcomes (e.g., Body Mass Index) will be compared across sex groups and significant differences will be included as covariates in the subsequent analyses. All analyses will be repeated and sex (male/female) will be added as a factor to the analyses.

c. Statistical plan including sample size justification and interim data analysis:

Since this will be the first study to examine the effect of cannabinoids on opioid-induced analgesia using a within-subject laboratory model of pain, there are no data available upon which a power analysis may be directly based. Therefore, we have used G-power to estimate our sample size. We estimate that a within-subject comparison using peak change from baseline as the primary outcome measure and comparing 6 medication conditions will yield power of 0.95 to detect a main effect at even a low effect size (0.2) by enrolling a sample size of 45. For each study, we are proposing to enroll 60 subjects to ensure we will have 50 study completers, and we will enroll equal quantities of men and women to examine sex-based differences in responding. This approach will result in an overall completion sample of 50 per study, with subsamples of 25 per group, which is consistent with other within-subject evaluations of drug effects. This sample size has been powered to support within-subject effects of study drug and between-subject effects of sex on study outcome measures.

d. Early stopping rules.

The safety of participants is a priority of BPRU. The largest potential risk of this study is cardiovascular in nature. This notion is based upon the results of a published study that reported an increase in heart rate and blood pressure

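### The Session 1 Drug Effect rating (0-100) is cut at an unexplained 20 points before it is screened by sex and used as a covariate; the continuous change would usually serve better

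*Combined protocol and SAP*

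**What the plan says.** Section 4.a (Session Measures) has participants rate drug-effect items "on a scale of 0 (none at all) to 100 (strongest possible"). Section 7.b (Secondary outcome variables) turns the Session 1 Drug Effect rating into a binary characteristic, "including a positive signal (defined as >20 points rating from baseline on VAS rating of Drug Effect from Session 1"). It places this variable with the demographic and drug-use characteristics that "will be compared across sex groups and significant differences will be included as covariates in the subsequent analyses". The next sentence of 7.b says that all analyses will be repeated with sex as a factor.

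Session 1 is the same for everyone: section 4.a randomizes the order of sessions "with the exception of Session 1, which will always be active hydromorphone + placebo". The signal is therefore each participant's response to hydromorphone without dronabinol.

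On numbers, section 7.c says "This approach will result in an overall completion sample of 50 per study, with subsamples of 25 per group". The project overview in 4.a says "This study will enroll 100 healthy adults, and will aim to complete 60 (30 men, 30 women) participants".

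The plan gives no reason for the 20-point threshold, specifies no between-sex comparison of the continuous Session 1 rating, and gives no distribution, SD or expected share of participants above the threshold.

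**The concern.** After the cut, changes of +21 and +90 count as the same response, while +19 and +21 count as opposite ones. Two steps then work with less than was measured. The screen is less likely to notice a real difference between the sexes in Session 1 response. And if the variable does enter the models, adjusting for a yes/no indicator removes only part of any imbalance in the underlying rating.

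This matters because the abstract gives sex differences in opioid response as a reason for analysing by sex, and the Session 1 signal is the only measure of response to hydromorphone without dronabinol that 7.b names for the sex analyses. What is at stake is the sensitivity of a covariate screen and the completeness of an adjustment.

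**Working it through.** **The plan's own power figure.** Section 7.c gives N = 45 for power 0.95 with 6 conditions and effect size 0.2. Assuming alpha 0.05, within-subject correlation 0.5 and sphericity, the noncentrality is f²Nm/(1-ρ) = 0.04 × 45 × 6 / 0.5 = 21.6 on 5 and 220 df, and power is 0.96. The figure reproduces, but it concerns the within-subject drug effect. The plan states no power for the sex comparison of Session 1 response.

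**Inputs.** From the documents: a 0-100 scale, a cut at >20 points from baseline, and 25 per sex (7.c) or 30 per sex (4.a). Assumed, because the documents are silent: a normal change with equal SD in both sexes, a shift between them, two-sided 5% tests, and a share p above the cut of 30% to 85%.

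**Information kept by the cut.** Relative to a comparison of means this is φ(z_p)² / [p(1-p)].

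| Share above cut | Calculation | Kept | Lost | 25 per sex is worth |
|---|---|---|---|---|
| 50% | 0.399² / 0.25 | 0.637 | 36% | 15.9 |
| 30% or 70% | 0.348² / 0.21 | 0.576 | 42% | 14.4 |
| 85% | 0.233² / 0.1275 | 0.426 | 57% | 10.7 |

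The 50% row is the best case, 2/π.

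**Power of the screen, 25 per sex.** For the t-test the noncentrality is d√(n/2); at d = 0.8 it is 0.8 × √12.5 = 2.83 on 48 df. For the binary version the shares above the cut are Φ(z_p ± d/2). At d = 0.8 and p = 50% these are 0.345 and 0.655, and the power of the chi-square test is found by exact enumeration.

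| Difference | t-test on change | Chi-square after cut (p = 30% to 85%) |
|---|---|---|
| 0.4 SD | 0.283 | 0.155 to 0.236 |
| 0.6 SD | 0.547 | 0.283 to 0.435 |
| 0.8 SD | 0.791 | 0.451 to 0.652 |

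With 30 per sex and 0.8 SD the figures are 0.861 against 0.509 to 0.694, so the gap does not depend on which sample size is right.

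**Adjustment.** Suppose the outcome is linear in the rating and the model contains sex and the indicator. The share of the imbalance left in the sex effect is 1 - b(p₁ - p₀)/d, where b is the pooled within-sex slope of the rating on the indicator. For small d this equals 1 - φ(z_p)²/[p(1-p)], that is 0.363, 0.424 and 0.574 for the three rows of the first table. At d = 0.8 it is 0.366, 0.432 and 0.585. Adjusting linearly for the continuous change leaves none under the same assumption.

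**Other shapes.** The 36% floor belongs to the normal model.
- Cut at the median, a logistic variable loses 18%, a t variable with 5 df loses 4%, and a uniform variable loses 67%.
- In a skewed simulation (20% zeros, otherwise gamma with shape 1.2 and scale 20, capped at 100; response multiplied by 1.4, 1.6 or 2.0 in one sex; 25 per sex) power was 0.163, 0.268 and 0.485 for the t-test and 0.134, 0.195 and 0.323 for the cut. A rank test gave 0.112, 0.167 and 0.299, slightly below the cut.
- In a simulated mix of non-responders near 0 and responders around 45 (SD 18), with the sexes differing in responder share, the cut won: 29% against 22% for shares of 50% and 70%, and 55% against 44% for 40% and 70%.

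**The case against.** The strongest objection is that the loss depends on a distribution that nobody has seen. A drug-effect rating in healthy volunteers could well split into people who feel the drug and people who do not, and then a threshold is a sensible summary. The exclusion criterion on failing to tell hydromorphone from placebo suggests that the protocol already thinks of drug detection as yes or no, although the plan does not link that criterion to the 20 points. This part stands: the 36% cannot be stated as a fact about this trial, and the advantage can reverse.

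A reader might also infer that the cut could make the trial miss a sex difference under Secondary Aim 1. The documents do not support that. The Aim concerns sex differences on study outcomes and is tested by adding sex as a factor; the signal is only screened as a possible covariate.

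Nor is 25 per sex firm. Section 4.a aims for 30 completers per sex, and Session 1 comes first, so its ratings would also exist for later dropouts.

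Finally, the screen is weak for modest differences either way: at 0.4 SD even the t-test has only 28% power. Choosing covariates by significance is a separate weakness that keeping the scale continuous does not cure.

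None of this supplies a reason for the 20-point threshold, or answers the incomplete adjustment, which also appeared in the skewed scenario (42% to 45% of the imbalance left).

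**Conclusion.** The point holds as a minor improvement. The plan reduces a 0-100 rating to an unexplained yes/no signal, screens it by sex and may adjust for it. Under a roughly normal change with equal SDs and a shift between the sexes, at least 36% of the information is lost. At 0.8 SD and 25 per sex, power drops from 79% to 45-65%. About 36-58% of an imbalance in the rating stays unadjusted when the outcome is linear in it. All of these figures rest on assumptions, because the documents give no distribution for the rating; with other shapes the loss may be smaller, larger or absent.

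The consequence is a less sensitive screen and a partial adjustment. It is not an invalid test of any Aim.

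**What to change.** In 7.b, make the analysed variable the continuous change from the Session 1 pre-dose baseline on the VAS Drug Effect item. Compare men and women by the mean difference with a 95% confidence interval; a rank test would not have gained anything in the skewed scenario. Wherever Session 1 response is used as a covariate, enter the continuous value and not the indicator. Report the proportion above 20 points in each sex descriptively. Since ratings are taken repeatedly after dosing, the sentence should also say which post-dose reading is meant; the present definition leaves that open. If the sponsor prefers the threshold, the plan should give the reason for it.

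The cost is a sentence or two of analysis wording, with no new data, visits or participants. A mean difference is slightly less simple to report than a percentage, and there is no gain if the ratings turn out to form two clear clusters.
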